11.1 General Efficacy Analysis Methodology

Unless otherwise specified, all the efficacy analyses will be based on the FAS.

All the tables and graphs will be presented overall and by previous treatment group unless otherwise specified.

All the confidence intervals (CIs) will be two-sided, 95% CIs.

Descriptive statistics for the absolute scores and the change from baseline scores for the efficacy variables will be presented by study week using all available observations (observed cases [OC] data). The tables will be repeated for LOCF values.

11.2 Exploratory Analysis of Efficacy

Changes from baseline in PANSS total score, PANSS subscale scores (PANSS Negative Symptoms subscale, PANSS Positive Symptoms subscale, PANSS General Psychopathology subscale, and PANSS Marder factors), NSA-4 total score, CGI-S score, QLS score, TooL score, WorQ score, PSP total score, and MSQ score will be analysed using a restricted maximum likelihood (REML)-based Mixed Models for Repeated Measurements (MMRM) approach. The analysis will be based on the FAS.

The model will include the following fixed effects: country and week as factors, baseline score as a continuous covariate, and baseline score-by-week interaction. An unstructured covariance structure will be used to model the within-patient errors. The Kenward-Roger approximation will be used to estimate denominator degrees of freedom.

The estimated mean changes from baseline will be reported with two-sided 95% confidence intervals.

The estimated mean change from baseline in PANSS total score by visit week will be plotted for the total group.

The SAS code for fitting the MMRM models is shown in [Appendix II](#).

For PANSS total score, PANSS Negative Symptoms subscale score, PANSS Positive Symptoms subscale score, PANSS Negative Symptoms Marder factor score, a further exploratory analysis will be presented where previous treatment and previous-treatment-by-week interaction are added as fixed effects to the model described above. For these analyses, the estimates from the MMRM analysis will be presented by previous treatment.

Tables displaying the counts and proportion of patients in remission according to the Andreasen symptoms remission criteria described in section [19.1.2](#) (simultaneous ratings of mild or less on items P1, G9, P3, P2, G5, N1, N4, and N6, see [Panel 4](#) and [Panel 5](#)) will be presented both by previous treatment and for the total group, for LOCF values only.

HEA items will be summarized overall and by previous treatment group for the Baseline Visit and the Primary Outcome/Withdrawal Visit based on the APTS.

12 Safety

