#### **17.8 Effectiveness Analyses**

Effectiveness assessment will be summarised descriptively using Observed Cases (OC). Summaries will be performed with respect to both Baseline I and Baseline II. On an exploratory basis, the maintenance of effectiveness will be analysed using Mixed Models for Repeated Measurements (MMRM).

Quality of life, treatment satisfaction and health care resource utilization will be summarised.

Based on the FAS and observed cases (OC), the effectiveness endpoints will be analysed using a mixed model for repeated measurements (MMRM) with an unstructured covariance structure. The model will include terms for country, baseline 1/2 score visit, and previous treatment.

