As mentioned in section 2, due to a higher-than-anticipated roll-over rate and a lower-than-anticipated attrition rate from study 16159A, only patients from study 16159A and 16323A are enrolled in the study and the majority of the patients enrolled are from study 16159A.

The 4 patients enrolled from study 16323A come from different treatment regimens than those from study 16159A. Therefore, data from these 4 patients will only be presented in listings, i.e. they will not contribute to any summary tables.

This also means that the definition of the previous treatment groups included in this document have been changed from what was defined in the study protocol to accurately reflect the treatment received in the lead-in study.

Another implication of this change is that the analysis sets defined in section 5 have been updated to facilitate the analyses as well as to make it possible to include the patients from 16323A in listings.

The clinical study protocol defines the baseline just prior to randomization in study 16159A as an additional baseline and specifies that summary tables will be prepared both with respect to that baseline and the baseline defined in this document. However, these additional summaries will not be created, as it is considered sufficient to evaluate the data captured in this long-term study alone.

The above change also means that the baseline term referring to baseline just prior to randomization in study 16159A is removed from all statistical models.

In the protocol, it is stated that separate displays of descriptive statistics will be prepared for patients only receiving daily dosing in study 16159B. This will not be done, as it is considered sufficient to provide the tables including all patients regardless of dosing regimen.

19 Details on Data Handling

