19.1.2 PANSS

The PANSS² is a clinician-rated scale designed to measure severity of psychopathology in adult patients with schizophrenia, schizoaffective disorders, and other psychotic disorders. It emphasises positive and negative symptoms.

The PANSS consists of 30 individual items. Each item is rated from 1 (symptom not present) to 7 (symptom extremely severe).

The PANSS is grouped into three subscales: Positive Symptoms subscale, Negative Symptoms subscale, and General Psychopathology subscale. Furthermore, the division of PANSS into the 5 PANSS Marder factors³ is used. The five factors are: Negative symptoms, Positive Symptoms, Disorganized Thought, Uncontrolled Hostility/Excitement, and Anxiety/Depression. The binary Andreasen score of remission will also be derived from the PANSS scores. If any of the items used in the derivation of the remission score are missing, the derived score is also set to missing.

The PANSS items and the derivation of the total score, the subscale scores, the factor scores, and the remission scores are described in [Panel 4](#) and [Panel 5](#).

Panel 4 PANSS Items and Subscales

PANSS Individual Item	PARAMCD	PANSS Individual Item	PARAMCD
Positive Scale		General Psychopathology Scale	
Delusions	PANSS01	Somatic concern	PANSS15
Conceptual disorganization	PANSS02	Anxiety	PANSS16
Hallucinatory behaviour	PANSS03	Guilt feelings	PANSS17
Excitement	PANSS04	Tension	PANSS18
Grandiosity	PANSS05	Mannerisms & posturing	PANSS19
Suspiciousness	PANSS06	Depression	PANSS20
Hostility	PANSS07	Motor retardation	PANSS21
Negative Scale		Uncooperativeness	PANSS22
Blunted affect	PANSS08	Unusual thought content	PANSS23
Emotional withdrawal	PANSS09	Disorientation	PANSS24
Poor rapport	PANSS10	Poor attention	PANSS25
Passive-apathetic social withdrawal	PANSS11	Lack of judgement & insight	PANSS26
Difficulty in abstract thinking	PANSS12	Disturbance of volition	PANSS27
Lack of spontaneity & flow of conversation	PANSS13	Poor impulse control	PANSS28
Stereotyped thinking	PANSS14	Preoccupation	PANSS29
		Active social avoidance	PANSS30

Panel 5 Derivation of PANSS Total Score and Subscales

PANSS Total Score and Subscales	Derivation
PANSS Total Score	Sum of all items PANSS01 to PANSS30
PANSS Positive Symptoms subscale score	Sum of items PANSS01 to PANSS07
PANSS Negative Symptoms subscale score	Sum of items PANSS08 to PANSS14
PANSS General Psychopathology subscale score	Sum of items PANSS15 to PANSS30

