19.1.8 Medication Satisfaction Questionnaire (MSQ)

The MSQ⁹ is a patient-rated scale designed and validated to assess the patient's satisfaction with his or her current antipsychotic medication. The MSQ consists of one item that is rated on a 7-point scale ranging from 1 (extremely dissatisfied) to 7 (extremely satisfied).

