Appendix II

SAS[®] Code

SAS® Code

The code for fitting the overall models mentioned in section 11.2 is given below. The variable CHG refers to the change from baseline value, NOMWEEK refers to the week variable, COUNTRY to the country variable, USUBJID to the subject identifier variable, and BASE refers to the baseline value.

```
proc mixed data = xxx order = internal method = reml;  
  class COUNTRY NOMWEEK USUBJID;  
  model CHG = COUNTRY NOMWEEK BASE BASE * NOMWEEK / ddfm = kr;  
  repeated NOMWEEK / subject = USUBJID type = un;  
  lsmeans NOMWEEK / cl alpha = 0.05;  
quit;
```

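### The SAP's main MMRM drops previous treatment without declaring it, so 12 of the 16 modelled efficacy scores have only a pooled model-based estimate

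*SAP*

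**What the plan says.** Protocol section 17.8 states that "the effectiveness endpoints will be analysed using a mixed model for repeated measurements (MMRM) with an unstructured covariance structure", without naming a subset of endpoints. It continues: "The model will include terms for country, baseline 1/2 score visit, and previous treatment". The baseline and visit terms run together in that sentence, but previous treatment is plainly listed.

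SAP section 11.2 specifies the main MMRM differently: "The model will include the following fixed effects: country and week as factors, baseline score as a continuous covariate, and baseline score-by-week interaction". The Appendix II code matches: "model CHG = COUNTRY NOMWEEK BASE BASE * NOMWEEK / ddfm = kr", with least-squares means requested by week only.

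SAP section 11.2 then adds a further exploratory model for four scores: PANSS total, PANSS Negative, PANSS Positive and the Marder negative factor. That model contains previous treatment and its interaction with week, and its estimates are shown by previous treatment.

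SAP section 18, which lists changes from the protocol, declares one model change: "The above change also means that the baseline term referring to baseline just prior to randomization in study 16159A is removed from all statistical models". It also says that the previous-treatment categories were redefined. It does not say that previous treatment left the main model.

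SAP section 11.1 makes overall and by-previous-treatment presentation the default for efficacy tables and graphs, and plans descriptive tables by week on observed cases and on LOCF.

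**The concern.** Previous treatment here is the arm a patient received in study 16159A. All patients start study 16159B on 10 mg/day (Protocol section 6.1 and Panel 3), so the three SAP groups start from different positions. Lu AF35700 10 mg patients continue, Lu AF35700 20 mg patients change dose, and RIS/OLZ patients change drug. Baseline is the last assessment in the lead-in study (SAP section 3.1).

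The mixture is hardest to interpret for the two patient-reported scales. MSQ is meant to "assess the patient's satisfaction with his or her current antipsychotic medication", and TooL measures the impact of side effects of antipsychotic treatment. For RIS/OLZ patients the change from baseline compares two drugs. For the others it follows the same drug over time. One pooled mean change answers neither question, and neither scale is among the four given the extended model.

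There is also a missing-data issue. Protocol section 5.1 plans for about 200 completers out of 400, so Week 52 estimates lean on the model. A variable that may predict both outcome and withdrawal is known for every patient in the FAS, yet is left out.

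**Working it through.** **Models side by side**

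| Source | Scores | Fixed effects |
|---|---|---|
| Protocol 17.8 | Effectiveness endpoints | Country, baseline score(s), visit, previous treatment |
| SAP 11.2 main model and Appendix II | All modelled scores | Country, week, baseline, baseline-by-week |
| SAP 11.2 further model | Four PANSS scores | Main model plus previous treatment and previous-treatment-by-week |

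SAP section 18 accounts for the loss of the lead-in baseline term, but not for the loss of previous treatment.

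**Count of scores.** SAP section 19.1.2 expands the Marder factors: "The five factors are: Negative symptoms, Positive Symptoms, Disorganized Thought, Uncontrolled Hostility/Excitement, and Anxiety/Depression".

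- Modelled: PANSS total (1) + subscales (3) + Marder factors (5) + NSA-4, CGI-S, QLS, TooL, WoRQ, PSP, MSQ (7) = 16.
- With previous treatment in some model: 4. Without: 16 − 4 = 12, namely PANSS General Psychopathology, four Marder factors and the seven other scales.
- Counting only scores named as endpoints in Protocol section 16.2 (no Marder factors): 1 + 3 + 7 = 11 modelled, 3 with the term, 8 without.

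**What pooling does to the estimate, with no missing data.** Let w be the RIS/OLZ share and d the difference in mean change between switchers and continuers. The pooled mean lies w·d from the continuers' mean and (1 − w)·d from the switchers'. The documents give neither w nor d. Assuming w between 1/3 and 1/2, the pooled mean lies only one third to one half of the way from continuers to switchers. With an assumed d of 2 to 5 points:

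- distance from continuers: 1/3 × 2 = 0.7 up to 1/2 × 5 = 2.5;
- distance from switchers: 1/2 × 2 = 1.0 up to 2/3 × 5 = 3.3.

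Such a d suits a wide scale. It does not suit MSQ or CGI-S, which run from 1 to 7.

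**What withdrawal could add.** Bias arises only if trajectory and withdrawal both depend on previous treatment. Even then, the unstructured covariance uses each patient's observed history and recovers part of the group difference. I checked this with a large-sample sequential-regression calculation on assumed inputs: three equal groups, SD 12, 15 visits, correlation 0.8 across three visits, withdrawal depending on group only.

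| RIS/OLZ v. other change | Completion | True pooled mean at Week 52 | Bias, linear trajectory | Bias, change reached by one third of follow-up |
|---|---|---|---|---|
| −7 v. −2 | 40% v. 60% | (−7 − 2 − 2)/3 = −3.7 | about 0.3 to 0.4 | about 0.2 |
| −10 v. −2 | 35% v. 60% | (−10 − 2 − 2)/3 = −4.7 | about 0.6 | about 0.3 to 0.4 |
| +3 v. −2 | 35% v. 60% | (3 − 2 − 2)/3 = −0.3 | about −0.4 | about −0.3 |

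In each case the estimate moves towards the group with more completers. With completion of 50% against 55% in the first row, the bias is about 0.1. On an MSQ-like scale (assumed SD 1.4, three visits, +0.8 against +0.2, completion 35% to 40% against 60%) it is at most about 0.05, on a true pooled mean of (0.8 + 0.2 + 0.2)/3 = 0.4.

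**The case against.** The strongest reply is that results by group are already planned. SAP section 11.1 tabulates change from baseline by week and previous treatment for every efficacy score, MSQ and TooL included. This stands: a reader might infer that the plan hides continuers and switchers from view, and it does not. What is missing is a likelihood-based estimate with a confidence interval; the by-group tables rest on observed cases and LOCF. If the section 11.1 default is meant to cover MMRM tables too, the main model and its code cannot produce the split.

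Second, the protocol lists previous treatment as a single term, with no interaction with visit and no promise of group estimates. This also stands. Restoring the protocol's model would adjust the weekly means but would not give separate trajectories, and for four scores the SAP already does more than the protocol asked. Extending that model is an improvement, not merely a restoration.

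Third, the Marder factors are not protocol endpoints, so 12 of 16 overstates the departure from the protocol. That is correct, and 8 of 11 is the figure for the departure itself.

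Fourth, a reader might carry the tenths of a point in the bias table over to the affected scores. The documents do not support that. The inputs are assumed and describe something like PANSS total, which already has the extended model. Six of the affected scales have only three post-baseline visits (SAP Panel 7), and an SD of 12 is impossible on a 1-to-7 scale.

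Finally, these are exploratory analyses in an uncontrolled safety study, with the model and code fully shown. That limits the consequence but does not remove the need to declare the change.

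**Conclusion.** The point holds in a limited form. Previous treatment is in the protocol's MMRM, is absent from the SAP's main model and code, and its removal is not declared in SAP section 18. As a result, 12 of 16 modelled scores, or 8 of 11 protocol-named scores, have only a pooled model-based estimate. That rests on the text and on a count, not on assumptions.

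The practical loss is greatest for MSQ and TooL, because RIS/OLZ patients' baseline reflects a different drug from their follow-up. A bias towards the group that stays is possible, but only if trajectory and withdrawal both differ by previous treatment. Its size cannot be obtained from the documents and is probably small. No figure in points should be attached to the affected scales.

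No primary safety conclusion is touched. The change is worth making because the variable is already collected and the SAP already specifies the model for four scores.

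**What to change.** Use the SAP's own extended model, with previous treatment and previous-treatment-by-week, for all 16 modelled scores. Report weekly estimates with 95% confidence intervals for Lu AF35700 10 mg, Lu AF35700 20 mg and RIS/OLZ, and for the total. Weight the total by each group's share of patients in the FAS. Equal weighting of the three groups, or weighting by the number of observations, would not give that total.

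Add an entry to SAP section 18 saying how the model differs from Protocol section 17.8, including the added interaction. If the sponsor prefers to keep the reduced main model, that section should state that previous treatment was removed, and why.

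The cost is one more CLASS variable, two more MODEL terms and the matching least-squares-means and weighting statements in Appendix II. There will be a few more model parameters and exploratory tables. No new data are needed.

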### 16.2 Exploratory Endpoint(s)

- Exploratory safety and tolerability endpoints:
  - Mean change from baseline in AIMS, BARS and mSAS total scores
  - C-SSRS categorisation
- Exploratory effectiveness endpoints:
  - Psychotic symptoms
    - Mean change from baseline in PANSS total score
    - Mean change from baseline in PANSS subscale scores (PANSS Negative Symptoms subscale, PANSS Positive Symptoms subscale, PANSS General Psychopathology subscale)
  - Negative symptoms
    - Mean change from baseline in NSA-4 total score
  - Global clinical impression
    - Mean change from baseline in CGI-S score
  - Andreason symptoms remission rate
    - Binary variable (Y/N) of remission rate (simultaneous ratings of mild or less on PANSS specific items: P1, G9, P3, P2, G5, N1, N4, and N6) at Week 52 Visit
  - Quality of life and functioning
    - Mean change from baseline in QLS score
    - Mean change from baseline in Tool score
    - Mean change from baseline in WorQ score
    - Mean change from baseline in PSP total score

- Treatment satisfaction
  - Mean change from baseline in MSQ score
- Health care resource used during the 52-week study period

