3.1 Definition of Baseline

The baseline value is the value captured at the Baseline Visit of study 16159B. For efficacy/safety assessments and blood/urine samples this will be the value captured at the Primary Outcome Visit of study 16159A or at the last day of the dosing period (Day 42) in study 16323A.

For baseline characteristics captured at screening of the lead-in study, the baseline value in this study is the one captured either at the screening or baseline visit of the lead-in-study,

whichever is later. An exception to this is blood sampling for CYP2D6 and CYP2C19 genotyping, which is performed at randomization for 16159A patients.

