4.2 Exploratory Endpoints

- Exploratory safety and tolerability endpoints:
 - Change from baseline in AIMS, BARS Global Clinical Assessment of Akathisia score (item 4) score and mSAS total score
 - C-SSRS
- Exploratory efficacy endpoints:
 - *Psychotic symptoms*
 - Change from baseline in PANSS total score
 - Change from baseline in PANSS subscale scores (PANSS Negative Symptoms subscale, PANSS Positive Symptoms subscale, PANSS General Psychopathology subscale)
 - *Negative symptoms*
 - Change from baseline in NSA-4 total score
 - Change from baseline in PANSS Marder factor score (negative symptoms)
 - *Global clinical impression*
 - Mean change from baseline in CGI-S score
 - *Andreasen symptoms remission*
 - Remission (simultaneous ratings of mild or less on PANSS specific items: P1, G9, P3, P2, G5, N1, N4, and N6) at Week 52 Visit
 - *Quality of life and functioning*
 - Change from baseline in QLS score
 - Change from baseline in ToolL score
 - Change from baseline in WorQ score
 - Change from baseline in PSP total score
 - *Treatment satisfaction*
 - Change from baseline in MSQ score
 - Health care resource used during the 52-week study period

5 Analysis Sets

The patients will be assigned to analysis sets based on IMP intake and post-baseline assessments of the efficacy variable(s) in the Treatment Period.

Due to a higher-than-anticipated roll-over rate and a lower-than-anticipated attrition rate from study 16159A, only patients from study 16159A and 16323A are enrolled in the study, i.e. no patients who have not previously participated in a study investigating Lu AF35700 are enrolled.

Only 4 patients from study 16323A are enrolled. Therefore, data from these will only be presented in listings, i.e. they will not contribute to any summary tables.

The sets of patients to be analysed are defined as follows:

- *all-patients-enrolled set* (APES) – all patients enrolled, including patients from study 16323A
- *all-patients-treated set* (APTS) – all patients from study 16159A who took at least one dose of Lu AF35700 in study 16159B
- *full-analysis set* (FAS) – all patients in the APTS (i.e. only patients from study 16159A are included) who had a valid baseline assessment and at least one valid post baseline assessment of PANSS total score in study 16159B.

Since this is an open-label study each patient will be classified according to these definitions based on information in data and no Classification Meeting will be held.

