7.2 Withdrawals

The number of patients who withdrew from treatment will be summarized overall and by previous treatment both by primary reason for withdrawal, and all reasons for withdrawal.

Patients who withdrew from treatment will be listed and the listing will include the reason type (primary or secondary reason for withdrawal from treatment), the reason, specification of other reason, previous treatment group, date of Visit 2, date of withdrawal from treatment, and number of days on IMP in this study. Note that patients can have more than one secondary reason for withdrawal from treatment so the listing will include both the primary reason for withdrawal from treatment and all reasons for withdrawal from treatment.

Kaplan-Meier failure plots of time to withdrawal from treatment will be presented for the total group. The time will be calculated from the date of first dose of IMP in this extension study (for handling of missing IMP start date, see section 19.3.1) to the date of completion or withdrawal from treatment. Patients who completed treatment will be regarded as censored.

All tables and graphs will be based on the APTS. Listings will be based on the APES.

8 Demographics and Baseline Characteristics

Demographics (sex, age, age group, race, and ethnicity); baseline characteristics (height, weight, BMI, and waist circumference); baseline disease characteristics (age – and years since diagnosis of schizophrenia, years since first – and number of antipsychotic treatments, number of psychiatric hospitalizations), social histories; and baseline efficacy variables (PANSS total and subscale scores, CGI-S score, and PSP total score) will be summarized overall and by previous treatment group. CGI-S will be summarized both as a continuous and a categorical variable.

Concurrent as well as relevant past medical, neurological, and psychiatric disorders at the lead-in study Screening Visit will be coded using the *Medical Dictionary for Regulatory Activities* (MedDRA) and summarized.

A concurrent medical, neurological, or psychiatric disorder is a disorder that is ongoing at the Screening Visit of the lead-in study. A past medical, neurological, or psychiatric disorder is a disorder that ended prior to the Screening Visit of the lead-in study.

Demographics and baseline characteristics will be summarized based on the APTS, and baseline efficacy variables will be summarized based on the FAS.

9 Recent and Concomitant Medication

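### Remission is defined at the Week 52 Visit and the protocol summarises effectiveness by observed cases, but the SAP tabulates remission by LOCF alone and does not declare the change

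*SAP*

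**What the plan says.** **Endpoint.** Remission requires eight named PANSS items all to be rated mild or lower. The definition in Protocol 16.2 ends "N4, and N6) at Week 52 Visit", and SAP 4.2 has the same time point. Both documents list remission among the exploratory effectiveness (SAP: efficacy) endpoints.

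**Data handling in the protocol.** Protocol 17.8 states: "Effectiveness assessment will be summarised descriptively using Observed Cases (OC". Protocol section 17 describes no LOCF analysis; the term appears only in the abbreviation list.

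**Data handling in the SAP.** SAP 11.1 gives observed-case tables by week for absolute and change scores, then adds: "The tables will be repeated for LOCF values". SAP 11.2 treats remission differently: counts and proportions are shown by previous treatment and "for the total group, for LOCF values only".

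**Missing items.** SAP 19.1.2: "If any of the items used in the derivation of the remission score are missing, the derived score is also set to missing". SAP 19.2.1 fills a missing visit with the last usable rating in the Treatment Period and does not carry baseline forward.

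**Analysis set and baseline.** SAP 5 requires, for the FAS, a valid baseline and "at least one valid post baseline assessment of PANSS total score in study 16159B". SAP 3.1 says of the baseline for efficacy assessments that "this will be the value captured at the Primary Outcome Visit of study 16159A" (or, for the few patients from 16323A, the last dosing day of that study).

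**The concern.** The endpoint asks who is in remission after 52 weeks of treatment. A table built only on LOCF answers a different question: who was in remission at the last usable rating, whenever that was. A patient who left after an early visit contributes that visit's status to a figure that SAP 4.2 leads the reader to take as Week 52 status.

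The rating-scale scores have an observed-case table beside the LOCF one, so a reader can separate the two. Remission does not. Because SAP 18 omits the departure, a reader who compares the report with the protocol will not be told that the method changed. What is at stake is the interpretability of one exploratory endpoint, not the safety conclusions.

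**Working it through.** The documents state no remission rate and no calculation on this point, so there is no figure to reproduce. The check compares the sections, then sets out the algebra.

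**Step 1: time point and method side by side.**

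| Item | Protocol | SAP |
|---|---|---|
| Time point | Week 52 Visit (16.2) | Week 52 Visit (4.2); 11.2 names no visit |
| Scores and changes | Observed cases (17.8) | Observed cases, repeated for LOCF (11.1) |
| Remission | Covered by the general observed-case rule (17.8) | LOCF only (11.2) |
| Declared as a change | – | Not in section 18 |

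SAP 18 covers the enrolled population, the four patients from 16323A, the previous-treatment groups, the analysis sets, the dropped earlier baseline with its model term, and the dropped daily-dosing displays. It says nothing about LOCF or remission.

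**Step 2: whose status is carried forward.** Withdrawn patients are the obvious group. Completers can be affected too. SAP Panel 3 allows 6 missing items for the PANSS total (6/30 = 20%) but 0 for remission. Take a completer with one of the eight items missing at Week 52. The PANSS total is still derived (1/30 = 3.3% missing) and enters the observed-case table for Week 52. The remission score is missing, so LOCF supplies an earlier visit's status.

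**Step 3: denominator.** FAS entry depends on the PANSS total, which tolerates missing items, whereas remission tolerates none. Baseline is not carried forward. An FAS patient can therefore have no LOCF remission value at all, and the SAP does not say how such a patient is counted.

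**Step 4: relation between the figures.** Among patients with a LOCF remission value, let c be the share with a usable Week 52 score, p the proportion in remission among them, and r the proportion in remission at the last rating among the rest.

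- Observed cases: p
- LOCF: c·p + (1 − c)·r
- Rated and in remission at Week 52, as a share of all: c·p
- LOCF minus observed cases: (1 − c)(r − p). It is negative if r < p, zero if r = p and positive if r > p.
- LOCF minus the share rated and in remission: (1 − c)·r, which is never negative.

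**Step 5: illustration with assumed rates.** None of p, r or c below is a result from the documents. They serve only to show that the sign can go either way.

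| c | p | r | LOCF | Observed cases | LOCF minus observed | Rated and in remission |
|---|---|---|---|---|---|---|
| 50% | 40% | 10% | 20 + 5 = 25% | 40% | −15 points | 20% |
| 50% | 40% | 50% | 20 + 25 = 45% | 40% | +5 points | 20% |
| 80% | 40% | 10% | 32 + 2 = 34% | 40% | −6 points | 32% |
| 80% | 40% | 50% | 32 + 10 = 42% | 40% | +2 points | 32% |

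From the LOCF figure alone, a reader cannot recover either p or c·p.

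**The case against.** The strongest reply is that this matters little. Remission is one exploratory, descriptive endpoint in an open-label safety study with no hypothesis test and no sample-size calculation. The restriction to LOCF is stated openly and the table will be labelled accordingly. The observed-case sentence in Protocol 17.8 is general and does not name remission. The extent of carry-forward is also partly visible elsewhere: the by-week PANSS tables will show how many patients had a total score at Week 52, and disposition will show completers. SAP 11.1 sets the FAS as the default population, so the denominator is not wholly open. Nothing in the documents suggests that missing single items are common.

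Most of this is fair and limits the weight of the point. It does not remove it. Remission is listed under the effectiveness endpoints that 17.8 governs, and labelling a table LOCF does not supply the Week 52 count. The number with a PANSS total at Week 52 is not the number with a remission score, because the missing-item rules differ, and neither gives the number in remission.

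A reader might go further and infer that LOCF will inflate remission. The documents do not support that: by Step 4, LOCF lies below observed cases whenever patients without a Week 52 score were less often in remission at their last rating.

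A reader might also take the planned 200 completers of 400 enrolled (Protocol 5.1) and infer a distortion of up to 50 points. That value is only the ceiling on LOCF minus the share rated and in remission. It would need every patient without a Week 52 score to be in remission at the last rating. The completion plan also assumed 100 newly recruited patients who were never enrolled, and it is a share of enrolled patients, not of the FAS.

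**Conclusion.** The point holds as a mismatch between endpoint and table, together with an undeclared change from the protocol. The only planned remission figure cannot say how many patients were in remission at Week 52, which is what both documents define.

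The size and direction of the difference from observed cases cannot be derived. That would need the remission proportions with and without a usable Week 52 score and the share with one. The SAP reports more than 500 patients but no updated completion figure. A claim that the choice of method outweighs sampling error would rest entirely on assumed rates, so it is not made here.

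The conclusion rests on two readings: that the general observed-case rule in Protocol 17.8 covers remission as a listed effectiveness endpoint, and that the table in SAP 11.2 is meant to report the Week 52 endpoint of SAP 4.2, since 11.2 names no visit. No error rate, sample size or primary safety summary is affected.

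**What to change.** 1. In SAP 11.2, add an observed-case remission table for Week 52 in the FAS, overall and by previous treatment. Show the count in remission, the number with a usable Week 52 remission score, and the FAS size. The reader can then form both the observed-case proportion and the proportion of the FAS rated and in remission.
2. Keep the LOCF table as supportive. Name its visit and state its denominator, including how FAS patients without any usable post-baseline remission score are counted.
3. List the use of LOCF for remission in SAP 18, with a reason.
4. Optionally, show remission status at baseline beside the Week 52 result. Patients enter at the end of the lead-in study and may already be in remission, yet SAP 8 limits its list to "baseline efficacy variables (PANSS total and subscale scores, CGI-S score, and PSP total score". Neither document requires this display, but it is cheap.

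The cost is some SAP wording and one extra table from PANSS data already scheduled at every visit. The downside is that the added figures may be less favourable: the proportion of the FAS rated and in remission cannot exceed the LOCF proportion, while the observed-case proportion may fall on either side of it.
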